## **5.12. Key Secondary Efficacy Analysis**

To control type I error, a graphical testing scheme as described in Section 5.3 will be used to compare treatments regarding the following selected secondary objectives (body weight, fasting blood glucose, and HbA1c target of <7.0%) once the primary objective has been achieved.

### **5.12.1. Analysis of Body Weight**

The evaluation of change from baseline in body weight will be performed using MMRM and ANCOVA models on the ITT population. The MMRM model, which will be primary for the change in weight, will include treatment, country, SGLT2 inhibitor dose (“low” versus “high”), metformin use (“yes” versus “no”), visit, baseline HbA1c strata ( $\leq 8.0\%$ , and  $> 8.0\%$ ), treatment-by-visit interactions as fixed effects, and baseline body weight as a covariate and patient as a random effect. The ANCOVA model with LOCF includes treatment, country, SGLT2 inhibitor dose (“low” versus “high”), metformin use (“yes” versus “no”), baseline HbA1c strata ( $\leq 8.0\%$ , and  $> 8.0\%$ ) as fixed effects, and baseline body weight as covariate. LS means, 95% CI, and the p-value will be presented for the treatment comparison.

### **5.12.2. Analysis of Fasting Blood Glucose**

Change from baseline in FBG will be summarized using the ITT population. This variable will be analyzed using the ANCOVA model with LOCF which includes treatment, country, SGLT2 inhibitor dose (“low” versus “high”), metformin use (“yes” versus “no”), baseline HbA1c strata ( $\leq 8.0\%$  and  $> 8.0\%$ ) as fixed effects, and baseline (FBG) as covariate.

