There will be 2 primary estimands to compare the placebo and the dulaglutide arms in terms of the primary measure of HbA1c change from baseline to 24 weeks. One primary estimand will be an efficacy estimand which will not use post-rescue data; the other primary estimand, requested by the US Food and Drug Administration (FDA), will be an ITT estimand (treatment regimen estimand) which will use post-rescue data. The efficacy estimand compares the benefit of the initially randomized treatments assuming all patients remained in the study and did not take additional or alternative antihyperglycemic medication. The estimate of mean change from baseline to endpoint reflects what would have been observed if patients stayed on their initially randomized treatments. The treatment-regimen estimand compares the benefit of treatment regimens as they are actually taken. The estimate of mean change from baseline to endpoint reflects what was actually observed regardless of use of any additional or alternative antihyperglycemic agents. Both estimands will use the same primary analysis model, and each will be tested at the full significance level of 0.05.

Analyses of the key secondary efficacy outcomes (percent to goal in HbA1c, FBG, body weight) and hypoglycemia will be performed on the full dataset with and without censoring data collected after rescue medication for any reason.

Unless otherwise noted, all tests of treatment effects will be conducted at a 2-sided alpha level of 0.05, and confidence intervals (CIs) will be calculated at 95%, 2-sided. All tests of interactions between treatment groups and other factors will be conducted at a 2-sided alpha level of 0.10.

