The baseline will be Visit 5, except for HbA1c. Patients who do not need stabilization will have blood drawn for baseline HbA1c at Visit 2, and those who need stabilization at Visit 4. For all variables except HbA1c, if baseline data are missing, the last nonmissing measurement taken prior to Visit 5 will be used for the baseline measurement. For HbA1c, if baseline data are missing, the imputation will be conducted only if an additional value between Visit 2 and randomization (patients not needing stabilization) or Visit 4 and randomization (patients needing stabilization) is collected. The endpoint for the primary analysis is defined as the change from baseline in HbA1c at 24 weeks (Visit 11). Key secondary endpoints are percent to goal in HbA1c (<7.0%) at 24 weeks and change from baseline in FBG (central laboratory) and body weight at 24 weeks.

Two analysis models will be used for the primary and key secondary continuous efficacy measures. The primary analysis will be mixed-model repeated measure (MMRM) analysis using restricted maximum likelihood (REML). An unstructured covariance structure will be used to model the within-patient errors. If this model fails to converge, the following covariance structures will be tested in order:

- Toeplitz with heterogeneity
- autoregressive with heterogeneity, by visit
- compound symmetry with heterogeneous variances by visit,
- Toeplitz
- autoregressive
- compound symmetry without heterogeneous variances, by visit

The first covariance structure that converges will be used.

The secondary analysis for the primary and key secondary continuous endpoints will be analysis of covariance (ANCOVA). Missing endpoints will be imputed with the last (postbaseline) observation carried forward (LOCF). The percentage of patients achieving the target HbA1c of <7.0% at 24 weeks will be analyzed using a longitudinal logistic regression with repeated measurements.

A graphical testing approach will be used to strongly control for type 1 error to test for superiority of each of the dulaglutide doses versus placebo at 24 weeks for the following

measures: (1) change from baseline in HbA1c, (2) change from baseline in FBG (central laboratory), (3) percent achieving HbA1c <7.0%, and (4) change from baseline in body weight.

[figure not shown]

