### 5.3. Graphical Testing Scheme

To control type I error, a graphical testing scheme (Bretz et al. 2011) presented in [Figure GBGE.5.1](#) will be used to compare treatments regarding selected secondary objectives once the primary objective has been achieved. In [Figure GBGE.5.1](#) the numbers in the circles indicate the fraction of alpha used for the first hypothesis tests. The numbers along the arrows represent the fraction of alpha from a hypothesis, if it is rejected, to allocate to the next hypothesis.

The graphical testing scheme will be performed for the efficacy estimand and the treatment regimen estimand (see [Section 5.1](#)) separately.

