**Figure GBGE.5.1. Graphical testing scheme for Study H9X-MC-GBGE.**

H1: Primary objective, superiority test of dulaglutide 1.5 mg versus placebo on hemoglobin A1c (HbA1c) change from baseline at 24 weeks.

H2: Primary objective, superiority test of dulaglutide 0.75 mg versus placebo on HbA1c change from baseline at 24 weeks.

H3: Superiority test of dulaglutide 1.5 mg versus placebo on HbA1c target 7.0% at 24 weeks.

H4: Superiority test of dulaglutide 0.75 mg versus placebo on HbA1c target 7.0% at 24 weeks.

H5: Superiority test of dulaglutide 1.5 mg versus placebo on body weight change from baseline at 24 weeks.

H6: Superiority test of dulaglutide 0.75 mg versus placebo on body weight change from baseline at 24 weeks.

H7: Superiority test of dulaglutide 1.5 mg versus placebo on FBG change from baseline at 24 weeks.

H8: Superiority test of dulaglutide 0.75 mg versus placebo on FBG change from baseline at 24 weeks.

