### 5.11.1. Additional Analyses for Primary Endpoint

The primary analysis model, MMRM, will be repeated for the PP population and the completer population as sensitivity analyses. If the conclusion differs from the analysis of the ITT population, the data and analyses will be further investigated.

The secondary analysis model will be an ANCOVA (only for excluding rescue data) for HbA1c change from baseline to 24 weeks (Visit 11), using a similar model as described above with

treatment, country, SGLT2 inhibitor dose (“low” versus “high”), and metformin use (“yes” versus “no”) as factors and baseline HbA1c as a covariate. Missing endpoints will be imputed with the LOCF using postbaseline data only using ITT population.

To investigate departure from the Missing At Random (MAR) assumption for the primary analysis for both efficacy and treatment regimen estimands, a sensitivity analysis using a particular missing not at random (MNAR) assumption will be performed. Specifically, a placebo multiple imputation (pMI) will be performed (Ayele et al. 2014), which assumes that the drug effect in missing data and post-rescue data in both the placebo arm and dulaglutide arm was like the observed effect in the placebo arm (excluding post-rescue data). This is essentially the “copy reference” approach as described in Carpenter et al. 2013. This approach is in essence assuming that the drug effect will decay over time, in accordance with the correlation structure implied by the data. Data imputed this way will be analyzed with the same MMRM model as the primary analysis. This particular MNAR assumption can be viewed as a “worst reasonable case” assessment of the two estimands..

For both the efficacy estimand and the treatment regimen estimand, a tipping point analysis will be performed in which the missing data are imputed with a MAR assumption. However, prior to analysis, in the dulaglutide arm the imputed values will be replaced by the imputed value plus delta. Multiple values of delta will be tried until the value at which the conclusion from the MMRM analysis changes.

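### Sections 5.2 and 5.12.2 of the SAP point to different models for fasting blood glucose, so the test behind H7 and H8 is not uniquely fixed

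*SAP*

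**What the plan says.** SAP Section 5.2 sets a general rule for the primary and key secondary continuous measures. On the first model it says "The primary analysis will be mixed-model repeated measure (MMRM) analysis using restricted maximum likelihood (REML"), and on the second "The secondary analysis for the primary and key secondary continuous endpoints will be analysis of covariance (ANCOVA"), with missing endpoints filled by LOCF. The same section lists FBG change among the key secondary endpoints.

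Section 5.12.2 says of FBG: "This variable will be analyzed using the ANCOVA model with LOCF". It lists terms for that model only. It does not mention MMRM, does not call ANCOVA primary or secondary, and does not announce a departure from Section 5.2.

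Section 5.12.1 gives body weight both models and ranks them: "The MMRM model, which will be primary for the change in weight".

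The hypotheses under Figure GBGE.5.1 name no model, for example "H7: Superiority test of dulaglutide 1.5 mg versus placebo on FBG change from baseline at 24 weeks". Section 5.3 adds that "The graphical testing scheme will be performed for the efficacy estimand and the treatment regimen estimand", separately for each. Section 5.2 also states that "Analyses of the key secondary efficacy outcomes (percent to goal in HbA1c, FBG, body weight) and hypoglycemia will be performed on the full dataset", both with and without censoring after rescue. The revision history in Section 3 lists no change to the FBG model.

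**The concern.** H7 and H8 sit inside a procedure for which Section 5.2 claims strong type I error control. Each therefore needs one pre-specified p-value per estimand. A statistician who follows Section 5.2 enters the MMRM result, and one who follows Section 5.12.2 literally enters the ANCOVA-LOCF result.

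The two models also treat a missing Week 24 value differently. Section 5.2 defines one estimand as the outcome had patients stayed on their randomized treatment, and the other as the outcome actually observed whatever else was taken. For a patient whose Week 24 FBG is missing, or is censored after rescue in the efficacy run, a carried-forward earlier value is neither of these. Read literally, Section 5.12.2 makes LOCF the confirmatory method in the treatment-regimen run as well.

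**Working it through.** **Comparison of the text**

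| Endpoint | Status | Models in its own section | Which is primary |
|---|---|---|---|
| HbA1c change (5.11, 5.11.1) | primary | MMRM; ANCOVA-LOCF | MMRM |
| Body weight change (5.12.1) | key secondary | MMRM; ANCOVA-LOCF | MMRM |
| FBG change (5.12.2) | key secondary | ANCOVA-LOCF | not stated |

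Section 5.2 covers all three rows, and only the FBG row departs from it. An FBG MMRM cannot simply be copied from another section either: the HbA1c MMRM in 5.11 has no baseline HbA1c stratum, while the body weight MMRM in 5.12.1 has one.

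**The SAP's own figures (Section 5.1)**

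Inputs: difference 0.55, SD 1.2, two-sided 0.025, power 90%, dropout 15%.

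- n per arm = 2 × (2.2414 + 1.2816)² × 1.2² / 0.55² = 118.2, rounded up to 119. The SAP states 120, at which power is 0.905 (0.901 with the noncentral t).
- 120 / 0.85 = 141.2, rounded up to 142 per arm; 3 × 142 = 426; 426 / 0.6 = 710 screened.

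These reproduce and are not in dispute. The SAP gives no power, SD or expected effect for FBG.

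**How many patients are involved**

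0.15 × 142 = 21.3 per arm; 0.15 × 426 = 63.9 in total. Those with an earlier postbaseline FBG enter ANCOVA-LOCF with that value.

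**How far LOCF can move the contrast**

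Let m be the missing fraction, equal in both arms and unrelated to outcome, with an earlier value available for each patient. Let d24 be the Week 24 effect and dL the effect at the last observed visit. Then

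LOCF contrast = (1 − m) × d24 + m × dL.

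Under this missingness MMRM targets d24, so the distance from d24 is also the expected gap between the two analyses.

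| m | dL/d24 = 0.5 | dL/d24 = 1 | dL/d24 = 1.5 |
|---|---|---|---|
| 0.15 (SAP dropout) | 0.85 + 0.075 = 0.925 | 1 | 0.85 + 0.225 = 1.075 |
| 0.25 (assumes 10 more points from rescue censoring) | 0.75 + 0.125 = 0.875 | 1 | 0.75 + 0.375 = 1.125 |

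A simulation of 4000 trials with 142 per arm agreed: 0.926 and 1.072 at m = 0.15, and 0.878 and 1.123 at m = 0.25.

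**Can the choice change a rejection? An illustration on assumed inputs**

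Assumptions: 142 per arm; three visits with correlations 0.5 to 0.6; effects at 0.4, 0.7 and 1.0 of the Week 24 effect; dropouts leaving after the first visit; dropout (dulaglutide/placebo) 15%/15%, 20%/10% or 10%/20%; two-sided 0.025; 3000 trials per setting. A two-sample test on LOCF values was compared with a likelihood-based analysis of the MMRM type.

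- Standardized Week 24 effects of 0.3 to 0.5: the two analyses reached different decisions in 1.5% to 9.5% of trials, and power differed by up to 6 points (0.759 against 0.819 at an effect of 0.4 and 20%/10% dropout).
- No effect: each rejected in 2.3% to 2.7% of trials, and they disagreed in about 1%.

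This shows only that the choice can matter. It does not predict a disagreement rate for this trial.

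**The case against.** The strongest reply is that each ordinary reading yields exactly one test. If the general rule governs, MMRM is the test and Section 5.12.2 merely adds the terms of the secondary model. If the endpoint section governs, ANCOVA-LOCF is the test. Fasting glucagon in Section 5.13.1 also has ANCOVA-LOCF alone, which suggests a deliberate choice for fasting laboratory measures. But the two readings give different tests, and the SAP does not say which section prevails. Glucagon is an other secondary endpoint, outside both the Section 5.2 rule and the graph, so its treatment may hint at intent but reconciles nothing.

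Three further points stand in part.

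- For HbA1c the SAP confines LOCF to one run: "The secondary analysis model will be an ANCOVA (only for excluding rescue data) for HbA1c change from baseline to 24 weeks". That limit is written for HbA1c only, and Section 5.13.1 runs ANCOVA-LOCF for glucagon with and without post-rescue data. The contrast is supporting context and does not by itself show an error.
- The ratio range of 0.5 to 1.5 and the extra 10 points for rescue are assumptions, and the symmetry of the result follows from them.
- Neither model is shown to inflate type I error when fixed in advance. The harm would come from choosing after seeing results, and Section 6.3 keeps the study team blinded until database lock.

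**Conclusion.** The concern holds. Sections 5.2 and 5.12.2 point to different analyses for FBG, so H7 and H8 lack a single pre-specified test under either estimand. This rests on the text and not on the calculation.

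In size it is moderate. At the SAP's 15% dropout, LOCF gives 92.5% to 107.5% of the Week 24 effect, or 87.5% to 112.5% at an assumed 25% missing or censored. Both ranges take last-visit effects of 0.5 to 1.5 times the Week 24 effect, equal missingness unrelated to outcome, and an earlier value for every affected patient. The shift is zero if the effect has stabilized. The FBG visit schedule, SD and rescue rate are not in the SAP, so no rejection or disagreement rate is claimed for this trial.

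H1 and H2 have their own stated model and are untouched. The ranking in Section 5.2 and the blinding lower the risk of a data-driven choice but do not remove the inconsistency. It should be fixed before unblinding.

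**What to change.** State in Section 5.12.2 that H7 and H8 are tested with the Section 5.2 MMRM and write out its terms: treatment, visit and their interaction; country; SGLT2 inhibitor dose group; metformin use; baseline HbA1c stratum; and baseline FBG as covariate. Apply it under each estimand, using the runs with and without post-rescue data that Section 5.2 already requires. Keep ANCOVA-LOCF and label it secondary, as for body weight.

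If the FBG visit schedule cannot support an MMRM, state and justify FBG as an exception in Section 5.2 before unblinding, and name the single model whose p-value enters the graph under each estimand.

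The cost is one or two sentences in the SAP and, if the schedule supports it, one standard model run under each estimand. No new data are needed.

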## 5. A Priori Statistical Methods

### 5.1. Determination of Sample Size

With 120 completers per arm, the study will have 90% power for demonstrating superiority of either dulaglutide 1.5 mg or 0.75 mg versus placebo in change from baseline in mean hemoglobin A1c (HbA1c) at 24 weeks, assuming a standard deviation (SD) of 1.2%, a difference between dulaglutide and placebo of 0.55%, and a 2-sided significance level of 0.025. Assuming that the dropout rate is 15% for the entire study period, the study will need to enroll at least approximately 142 patients in each arm for a total of 426 patients enrolled. Assuming a screen fail rate of 40%, a total of approximately 710 patients will be screened to meet these enrollment number requirements.

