## 5.11. Primary Efficacy Analysis

The primary outcome is the difference in HbA1c mean change from baseline to 24 weeks in the ITT population. The primary hypothesis of interest in this placebo-controlled study is whether dulaglutide has superior efficacy compared to placebo, in patients already treated with SGLT2 inhibitors.

The primary analysis model will be an MMRM for HbA1c change from baseline to 24 weeks in the ITT population (Visit 11) with treatment, country, SGLT2 inhibitor dose ("low" versus "high"), metformin use ("yes" versus "no"), visit and treatment-by-visit as fixed effects, baseline HbA1c as a covariate, and patient as a random effect.

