#### **5.15.2.2. Percentage of Patients Receiving Rescue Medication due to Severe, Persistent Hyperglycemia**

Frequency counts and percentage of patients receiving rescue medication due to severe persistent hyperglycemia will be presented using ITT population. Fisher's exact test will be applied to compare treatments on the proportion of patients receiving rescue medication due to severe persistent hyperglycemia. Time to receiving rescue medication due to severe persistent hyperglycemia will be analyzed to compare treatment groups using a semi-parametric proportional hazard Cox regression model with treatment, country, SGLT2 inhibitor dose ("low" versus "high"), metformin use ("yes" versus "no"), baseline HbA1c strata ( $\leq 8.0\%$  and  $> 8.0\%$ ) as fixed effects, and baseline HbA1c as a covariate. A Kaplan-Meier curve will be plotted for both treatments on the same graph, for presentation purposes. These same reports will be also provided for patients meeting criteria for severe persistent hyperglycemia, irrespective of whether they received rescue therapy while in the trial or not.

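### FBG tests (H7, H8): baseline HbA1c enters the model only as a split at 8.0%; adding the continuous value could recover a little precision (optional)

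*SAP*

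**What the plan says.** H7 and H8 in the graphical testing scheme (SAP Figure GBGE.5.1) are the FBG comparisons of each dulaglutide dose with placebo. Section 5.12.2 gives the FBG model as an ANCOVA with LOCF. Its factors include baseline HbA1c in two strata, cut at 8.0%. The listed terms enter "as fixed effects, and baseline (FBG) as covariate", so FBG's own baseline is continuous and HbA1c is not.

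Other models in the SAP treat HbA1c as follows:

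- **Body weight (5.12.1; H5 and H6).** The same two strata are used, "and baseline body weight as a covariate and patient as a random effect".
- **Primary HbA1c model (5.11).** HbA1c is continuous: "baseline HbA1c as a covariate, and patient as a random effect". The HbA1c target models (5.12.3, 5.13.2) also use it continuously.
- **Time to rescue (5.15.2.2).** The Cox model carries both forms. The strata are among the terms entered "as fixed effects, and baseline HbA1c as a covariate".

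The SAP gives no reason for using only the split in 5.12.2.

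**The concern.** Section 5.7 treats HbA1c outside 7.0% to 9.5% at the qualifying visits as an important deviation, so most baseline values should lie in that range. With a single cut at 8.0%, patients at 8.1% and 9.5% get the same adjustment. HbA1c reflects average glycaemia over time, and FBG is one reading. It is therefore plausible that HbA1c carries some information about later FBG that baseline FBG does not. Whatever the split discards of that information stays in the residual variance.

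H7 and H8 are alpha-controlled tests, so a slightly larger standard error slightly reduces the chance of rejecting them. Chance imbalance in HbA1c within a stratum is the same loss seen from another side and should not be counted as a second harm. At stake is efficiency only; the validity of the tests is not in question.

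**Working it through.** **1. The plan's own figures.** Section 5.1 sizes the trial on HbA1c, "assuming a standard deviation (SD) of 1.2%, a difference between dulaglutide and placebo of 0.55" percentage points, at "a 2-sided significance level of 0.025", for 90% power: "With 120 completers per arm".

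- z(0.9875) + z(0.90) = 2.2414 + 1.2816 = 3.5230.
- n = 2 × 3.5230² × (1.2/0.55)² = 118.2, so 119 per arm (stated 120).
- Power at 120: 0.55 / (1.2 × √(2/120)) = 3.550; 3.550 − 2.241 = 1.309; Φ(1.309) = 90.5% (stated 90%).
- Enrolment: 120/0.85 = 141.2, so 142 per arm; 3 × 142 = 426.

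These reproduce. They concern HbA1c only. The SAP states no SD, effect size, correlation or power for FBG.

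**2. How much HbA1c information the split keeps.** Let k be the squared correlation of HbA1c with the indicator of being above 8.0%. Over 7.0% to 9.5%, under assumed distributions:

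- uniform: 0.72
- truncated normal, mean 7.8, SD 0.7: 0.68
- truncated normal, mean 8.0, SD 0.65: 0.67
- truncated normal, mean 8.3, SD 0.7: 0.63

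A normal variable split at its median gives 2/π = 0.64. So k is about 0.63 to 0.72.

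**3. Cost in residual variance.** Let r be the partial correlation of continuous HbA1c with Week 24 FBG, given the other covariates including baseline FBG. Then

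variance with split / variance with continuous HbA1c = (1 − k r²)/(1 − r²).

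Example: k = 0.64, r = 0.3 gives (1 − 0.0576)/0.91 = 1.0356.

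**4. Check by simulation.** The formula ignores that HbA1c and baseline FBG are correlated. It was therefore checked with 400,000 simulated patients, baseline FBG in the model, HbA1c truncated normal (mean 8.0, SD 0.65, about 53% above 8.0%), and an assumed HbA1c–FBG correlation of 0.4 or 0.6. The patient equivalent is 142 × (variance ratio − 1).

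| Assumed r | Variance ratio, formula (k = 0.70 to 0.64) | Variance ratio, simulated (corr. 0.4 / 0.6) | SE ratio, simulated | Patients per arm of 142 |
|---|---|---|---|---|
| 0 | 1 | – | – | 0 |
| 0.1 | 1.0030 to 1.0036 | 1.0033 / 1.0046 | 1.0017 / 1.0023 | 0.5 / 0.7 |
| 0.2 | 1.0125 to 1.0150 | 1.0157 / 1.0181 | 1.0078 / 1.0090 | 2.2 / 2.6 |
| 0.3 | 1.0297 to 1.0356 | 1.0358 / 1.0425 | 1.0177 / 1.0210 | 5.1 / 6.0 |

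**5. Power.** Take as a benchmark a test with 90% power under the continuous model at two-sided 0.025. With the formula's ratios, the split leaves 89.9% at r = 0.1, 89.5% to 89.6% at r = 0.2, and 88.9% to 89.1% at r = 0.3. At the largest simulated ratio, 3.5230/1.0210 − 2.2414 = 1.209, and Φ(1.209) = 88.7%. The loss is thus about 1 point at r = 0.3 and less below that.

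**The case against.** The strongest reply is that the SAP follows a consistent rule. Each continuous outcome has its own baseline as a continuous covariate, and outcomes other than HbA1c add the HbA1c strata: body weight, FBG, glucagon, SMPG and QT all do so. HbA1c is continuous in 5.11 and 5.12.3 because there it is the outcome's own baseline. A reader might infer from the contrast with the primary model that 5.12.2 is inconsistent or mistaken. The documents do not support that. The Cox model is also only a partial precedent, because time to rescue has no baseline value of its own. Section 5.16 goes the other way: when the HbA1c strata are the subgroup, it omits the continuous value. This stands. The case for the extra term rests on efficiency alone.

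Second, the word strata suggests a randomisation factor, although this document does not say so. If it is one, keeping it in the model is standard practice. That argues against replacing the factor. It does not argue against adding a covariate beside it.

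Third, baseline FBG is already in the model and should remove much of the explainable variance. The loss is only what continuous HbA1c explains beyond baseline FBG, the split and the other terms. Nothing in the SAP favours r = 0.3 over 0.1 or zero. This also stands, so the claim has to be conditional.

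A reader might also infer that the body weight tests, H5 and H6, lose precision in the same way. The argument about average glycaemia and the simulation both concern FBG. No mechanism or calculation is offered for weight, so no loss is claimed there.

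**Conclusion.** The point holds as a small, conditional gain in precision for FBG (H7, H8). The analysis as written is unbiased, controls type I error, and leaves the graphical procedure untouched. With partial correlations of 0.1 to 0.3, the split's standard error is about 0.2% to 2% larger than it would be with continuous HbA1c. If r is zero, nothing is lost.

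The size rests on three assumptions that the SAP neither confirms nor excludes: the partial correlation, the spread of HbA1c within 7.0% to 9.5%, and the correlation of HbA1c with baseline FBG. A materially larger loss would need a much stronger partial correlation. At r = 0.5 the formula gives residual variance 10% to 12% higher, but nothing in the document supports such a value. It would therefore be too strong to say outright that the FBG standard errors are larger than the data require.

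**What to change.** In section 5.12.2, keep the two-level HbA1c factor and add continuous baseline HbA1c as a covariate alongside baseline FBG. For consistency the same term may be added in 5.12.1; this is harmless, but no meaningful gain is shown for body weight.

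The cost is a few words and one degree of freedom among 426 planned patients. Endpoint, population, hypotheses and testing order stay the same. The change should be made before database lock, while the study team is blinded (section 6.3).

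A separate matter touches the same sentence. Section 5.2 makes MMRM primary for the key secondary continuous measures, while 5.12.2 describes only ANCOVA with LOCF. The covariate belongs in whichever model is confirmed as the test of H7 and H8.
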